*[Implementation note: Systemic symptoms presented will be fever, feverishness, fatigue, malaise, myalgia, or headache. Local symptoms presented will be irritation of the oral cavity or tongue, facial nerve disturbance, diarrhea, nausea, vomiting, or abdominal discomfort.]*

**Table 126: Number and Percentage of Subjects Experiencing Solicited Events by Symptom, Severity, Dose, Day Post Dosing, and Treatment Group – Cohort D: Sublingual 25 µg dmLT, Dose 2**

*[Implementation note: Systemic symptoms presented will be fever, feverishness, fatigue, malaise, myalgia, or headache. Local symptoms presented will be irritation of the oral cavity or tongue, facial nerve disturbance, diarrhea, nausea, vomiting, or abdominal discomfort.]*

**Table 127: Number and Percentage of Subjects Experiencing Solicited Events by Symptom, Severity, Dose, Day Post Dosing, and Treatment Group – Cohort D: Sublingual 25 µg dmLT, Dose 3**

*[Implementation note: Systemic symptoms presented will be fever, feverishness, fatigue, malaise, myalgia, or headache. Local symptoms presented will be irritation of the oral cavity or tongue, facial nerve disturbance, diarrhea, nausea, vomiting, or abdominal discomfort.]*

**Table 128: Number and Percentage of Subjects Experiencing Solicited Events by Symptom, Severity, Dose, Day Post Dosing, and Treatment Group – All Sublingual Cohorts: Placebo Dose 1**

*[Implementation note: Systemic symptoms presented will be fever, feverishness, fatigue, malaise, myalgia, or headache. Local symptoms presented will be irritation of the oral cavity or tongue, facial nerve disturbance, diarrhea, nausea, vomiting, or abdominal discomfort.]*

**Table 129: Number and Percentage of Subjects Experiencing Solicited Events by Symptom, Severity, Dose, Day Post Dosing, and Treatment Group – All Sublingual Cohorts: Placebo, Dose 2**

*[Implementation note: Systemic symptoms presented will be fever, feverishness, fatigue, malaise, myalgia, or headache. Local symptoms presented will be irritation of the oral cavity or tongue, facial nerve disturbance, diarrhea, nausea, vomiting, or abdominal discomfort.]*

**Table 130: Number and Percentage of Subjects Experiencing Solicited Events by Symptom, Severity, Dose, Day Post Dosing, and Treatment Group – All Sublingual Cohorts: Placebo, Dose 3**

*[Implementation note: Systemic symptoms presented will be fever, feverishness, fatigue, malaise, myalgia, or headache. Local symptoms presented will be irritation of the oral cavity or tongue, facial nerve disturbance, diarrhea, nausea, vomiting, or abdominal discomfort.]*

**Table 131: Number and Percentage of Subjects Experiencing Solicited Events by Symptom, Severity, Dose, Day Post Dosing, and Treatment Group – Cohort E: Intradermal 0.3 µg dmLT, Dose 1**

*[Implementation note: Systemic symptoms presented will be fever, feverishness, fatigue, malaise, myalgia, headache, diarrhea, nausea, vomiting, or abdominal discomfort. Local symptoms presented will be injection site pain, redness, swelling, bruising, itching, hypo/hyper pigmentation and induration, vesicles or hardened mass.]*

**Table 132: Number and Percentage of Subjects Experiencing Solicited Events by Symptom, Severity, Dose, Day Post Dosing, and Treatment Group – Cohort E: Intradermal 0.3 µg dmLT, Dose 2**

*[Implementation note: Systemic symptoms presented will be fever, feverishness, fatigue, malaise, myalgia, headache, diarrhea, nausea, vomiting, or abdominal discomfort. Local symptoms presented will be injection site pain, redness, swelling, bruising, itching, hypo/hyper pigmentation and induration, vesicles or hardened mass.]*

**Table 133: Number and Percentage of Subjects Experiencing Solicited Events by Symptom, Severity, Dose, Day Post Dosing, and Treatment Group – Cohort E: Intradermal Placebo, Dose 1**

*[Implementation note: Systemic symptoms presented will be fever, feverishness, fatigue, malaise, myalgia, headache, diarrhea, nausea, vomiting, or abdominal discomfort. Local symptoms presented will be injection site pain, redness, swelling, bruising, itching, hypo/hyper pigmentation and induration, vesicles or hardened mass.]*

**Table 134: Number and Percentage of Subjects Experiencing Solicited Events by Symptom, Severity, Dose, Day Post Dosing, and Treatment Group – Cohort E: Intradermal Placebo, Dose 2**

*[Implementation note: Systemic symptoms presented will be fever, feverishness, fatigue, malaise, myalgia, headache, diarrhea, nausea, vomiting, or abdominal discomfort. Local symptoms presented will be injection site pain, redness, swelling, bruising, itching, hypo/hyper pigmentation and induration, vesicles or hardened mass.]*

**Table 135: Number and Percentage of Subjects Experiencing Solicited Events for Dose 1 Compared with Dose 2 by Treatment Group**

Treatment Group		Dose 2 – Subjects with No Symptoms	Dose 2 – Subjects with Mild or Greater Symptoms	Dose 2 – Total Number of Subjects
Systemic Symptoms				
Cohort A: Oral 5 µg dmLT	Dose 1 Subject with No Symptoms	x (%)	x (%)	x (%)
	Dose 1 Subjects with Mild or Greater Symptoms	x (%)	x (%)	x (%)
	Dose 1 Total Number of Subjects	x (%)	x (%)	x (100%)
Cohort B: Oral 25 µg dmLT	Dose 1 Subject with No Symptoms			
	Dose 1 Subjects with Mild or Greater Symptoms			
	Dose 1 Total Number of Subjects			
All Oral Cohorts: Placebo	Dose 1 Subject with No Symptoms			
	Dose 1 Subjects with Mild or Greater Symptoms			
	Dose 1 Total Number of Subjects			
Cohort C: Sublingual 5 µg dmLT	Dose 1 Subject with No Symptoms			
	Dose 1 Subjects with Mild or Greater Symptoms			
	Dose 1 Total Number of Subjects			
Cohort D: Sublingual 25 µg dmLT	Dose 1 Subject with No Symptoms			
	Dose 1 Subjects with Mild or Greater Symptoms			
	Dose 1 Total Number of Subjects			
All Sublingual Cohorts: Placebo	Dose 1 Subject with No Symptoms			
	Dose 1 Subjects with Mild or Greater Symptoms			
	Dose 1 Total Number of Subjects			
Cohort E: Intradermal 5 µg dmLT	Dose 1 Subject with No Symptoms			
	Dose 1 Subjects with Mild or Greater Symptoms			
	Dose 1 Total Number of Subjects			
Cohort E: Intradermal Placebo	Dose 1 Subject with No Symptoms			
	Dose 1 Subjects with Mild or Greater Symptoms			
	Dose 1 Total Number of Subjects			

Treatment Group		Dose 2 – Subjects with No Symptoms	Dose 2 – Subjects with Mild or Greater Symptoms	Dose 2 – Total Number of Subjects
Local Symptoms				
Cohort A: Oral 5 µg dmLT	Dose 1 Subjects with No Symptoms	x (%)	x (%)	x (%)
	Dose 1 Subjects with Mild or Greater Symptoms	x (%)	x (%)	x (%)
	Dose 1 Total Number of Subjects	x (%)	x (%)	x (100%)
Cohort B: Oral 25 µg dmLT	Dose 1 Subjects with No Symptoms			
	Dose 1 Subjects with Mild or Greater Symptoms			
	Dose 1 Total Number of Subjects			
All Oral Cohorts: Placebo	Dose 1 Subjects with No Symptoms			
	Dose 1 Subjects with Mild or Greater Symptoms			
	Dose 1 Total Number of Subjects			
Cohort C: Sublingual 5 µg dmLT	Dose 1 Subject with No Symptoms			
	Dose 1 Subjects with Mild or Greater Symptoms			
	Dose 1 Total Number of Subjects			
Cohort D: Sublingual 25 µg dmLT	Dose 1 Subject with No Symptoms			
	Dose 1 Subjects with Mild or Greater Symptoms			
	Dose 1 Total Number of Subjects			
All Sublingual Cohorts: Placebo	Dose 1 Subject with No Symptoms			
	Dose 1 Subjects with Mild or Greater Symptoms			
	Dose 1 Total Number of Subjects			
Cohort E: Intradermal 5 µg dmLT	Dose 1 Subject with No Symptoms			
	Dose 1 Subjects with Mild or Greater Symptoms			
	Dose 1 Total Number of Subjects			
Cohort E: Intradermal Placebo	Dose 1 Subject with No Symptoms			
	Dose 1 Subjects with Mild or Greater Symptoms			
	Dose 1 Total Number of Subjects			

Note: Denominators for percentages are the number of subjects in the Safety Population who received the first and second dose. [x] subjects did not get the second dose and are not included in this table.

Tables with similar format:

**Table 136: Number and Percentage of Subjects Experiencing Solicited Events for Dose 1 Compared with Dose 3 by Treatment Group**

*[Implementation note: Footnote will be “Note: Denominators for percentages are the number of subjects in the Safety Population who received the first and third dose. [x] subjects did not get the third dose and are not included in this table.”]*

**Table 137: Number and Percentage of Subjects Experiencing Solicited Events for Dose 2 Compared with Dose 3 by Treatment Group**

*[Implementation note: Footnote will be “Note: Denominators for percentages are the number of subjects in the Safety Population who received the second and third dose. [x] subjects did not get the third dose and are not included in this table.”]*

**14.3.1.2 Unsolicited Adverse Events****14.3.2 Listing of Deaths, Other Serious and Significant Adverse Events****Table 138: Listing of Serious Adverse Events**

Adverse Event	Associated with Dose No.	No. of Days Post Associated Dose (Duration)	No. of Days Post Dose the Event Became Serious	Reason Reported as an SAE	Severity	Relationship to Study Treatment	If Not Related, Alternative Etiology	Action Taken with Study Treatment	Subject Discontinued Due to AE	Outcome	MedDRA System Organ Class	MedDRA Preferred Term
Subject ID: , Treatment Group: , AE Number:												
Comments:												
Subject ID: , Treatment Group: , AE Number:												
Comments:												

**Table 139: Listing of Non-Serious, Unsolicited, Moderate or Severe Adverse Events**

Adverse Event	Associated with Dose No.	No. of Days Post Associated Dose (Duration)	Severity	Relationship to Study Treatment	If Not Related, Alternative Etiology	Action Taken with Study Treatment	Subject Discontinued Due to AE	Outcome	MedDRA System Organ Class	MedDRA Preferred Term
Subject ID: , Treatment Group: , AE Number:										
Comments:										
Subject ID: , Treatment Group: , AE Number:										
Comments:										

---

#### **14.3.3 Narratives of Deaths, Other Serious and Significant Adverse Events**

(not included in SAP, but this is a placeholder for the CSR)

**14.3.4 Abnormal Laboratory Value Listings (by Subject)****Table 140: Listing of Abnormal Laboratory Results - Chemistry**

Subject ID	Treatment Group	Sex	Age (years)	Planned Time Point	Actual Study Day	Laboratory Parameter (Units)	Result (Severity)	Relationship to Treatment	If Not Related, Alternate Etiology	Action Taken with Study Treatment	Subject Discontinued Due to Result?

**Table 141: Listing of Abnormal Laboratory Results - Hematology**

Subject ID	Treatment Group	Sex	Age (years)	Planned Time Point	Actual Study Day	Laboratory Parameter (Units)	Result (Severity)	Relationship to Treatment	If Not Related, Alternate Etiology	Action Taken with Study Treatment	Subject Discontinued Due to Result?

### 14.3.5 Displays of Laboratory Results

#### 14.3.5.1 Chemistry Results

**Table 142: Laboratory Results by Parameter, Maximum Severity, Time Point, and Treatment Group – Any Chemistry Parameter**

Time Point	Treatment Group	N	None		Mild / Grade 1		Moderate/ Grade 2		Severe/ Grade 3		Missing	
			n	%	n	%	n	%	n	%	n	%
Baseline	Cohort A: Oral 5 µg dmLT	x	x	xx	x	xx	x	xx	x	xx	x	xx
	Cohort B: Oral 25 µg dmLT											
	All Oral Cohorts: Placebo											
	Cohort C: Sublingual 5 µg dmLT											
	Cohort D: Sublingual 25 µg dmLT											
	All Sublingual Cohorts: Placebo											
	Cohort E: Intradermal 0.3 µg dmLT											
	Cohort E: Intradermal Placebo											
7 Days Post-Dose 3 a	Cohort D: Sublingual 25 µg dmLT											
	Cohort D: Sublingual Placebo											
28 Days Post-Dose 3 b	Cohort A: Oral 5 µg dmLT											
	Cohort B: Oral 25 µg dmLT											
	All Oral Cohorts: Placebo											
	Cohort C: Sublingual 5 µg dmLT											
	Cohort D: Sublingual 25 µg dmLT											
	All Sublingual Cohorts: Placebo											
Max Severity Post Baseline	Cohort A: Oral 5 µg dmLT											
	Cohort B: Oral 25 µg dmLT											
	All Oral Cohorts: Placebo											
	Cohort C: Sublingual 5 µg dmLT											
	Cohort D: Sublingual 25 µg dmLT											
	All Sublingual Cohorts: Placebo											
	Cohort E: Intradermal 0.3 µg dmLT											
	Cohort E: Intradermal Placebo											

Note: The “Max Post Baseline” rows indicate the maximum severity experienced by each subject at any time point post baseline, including unscheduled assessments. N=Number of subjects in the Safety Population

a Day 36 for Oral & Sublingual Cohorts; Day 50 for Intradermal Cohort. Albumin was not evaluated at this visit.

b Day 57 for Oral & Sublingual Cohorts; Day 71 for Intradermal Cohort

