7.3.5 VISIT 6 (~1 week post-dose 3 \pm 1 day)

- Confirm ongoing consent prior to performing any study procedures. Conduct eligibility review. Review any AEs or SAEs that have occurred since the last visit as well as update the medical history and concomitant medications as necessary
 - Assess for injection site necrosis within 7 days of vaccination.
 - Assess for urticaria, laryngospasm, bronchospasm, or anaphylaxis determined to be related to vaccine and within 7 days of vaccination.
 - Assess for participants experience facial nerve neuropathy, confirmed by an investigator and determined to be related to vaccine.
- Record oral temperature, pulse, and blood pressure
- Targeted physical examination, if indicated based on review of medical history
- Collect approximately 22 mL of venous blood:
 - 2 mL for clinical safety labs: ALT (also known as SGPT), total bilirubin, and creatinine
 - 2 mL for serum ELISA and neutralization assays
 - 2 mL for ASC assay
 - 2 mL for ALS assay
 - 2 mL for ASC with homing

- 12 mL for cryopreservation of PBMC, for memory B cell (5 mL) and effector T cell assays (7 mL)
- Collect plasma from PBMC tubes
- Collect stool (approximately 4 gm) and saliva (approximately 2 mL) for IgA assay.
- 1-2 gm of stool frozen at $-80^{\circ}\text{C} \pm 15^{\circ}\text{C}$ for future use microbiome studies
- Collect memory aid/reactogenicity information
- Provide stool sample collection container and instructions on how to collect stool sample
- Provide instructions to women participants to avoid pregnancy through the 28 days from receipt of the last dose of vaccine.
- Confirm date and time for Visit 7

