7.3.6 VISIT 7 (~4 weeks post-dose 3 (window ± 3 days)

- Confirm ongoing consent prior to performing any study procedures. Conduct eligibility review. Review any AEs or SAEs that have occurred since the last visit as well as update the medical history and concomitant medications as necessary
 - Assess for injection site necrosis within 7 days of vaccination.
 - Assess for urticaria, laryngospasm, bronchospasm, or anaphylaxis determined to be related to vaccine and within 7 days of vaccination.
 - Assess for participants experience facial nerve neuropathy, confirmed by an investigator and determined to be related to vaccine.
- Record oral temperature, pulse, and blood pressure
- Targeted physical examination, if indicated based on review of medical history
- Collect approximately 17mL of venous blood:
 - 2 mL for clinical safety labs: CBC with differential for WBC, Hg, ANC, platelets; creatinine, albumin, and ALT
 - 3 mL for serum ELISA and neutralization assays
 - 12 mL for cryopreservation of PBMC, for memory B cell (5 mL) and effector T cell assays (7 mL)
 - Collect plasma from PBMC tubes
- Collect stool (approximately 4 gm) and saliva (approximately 2 mL) for IgA assay.
- 1-2 gm of stool frozen at $-80^{\circ}\text{C} \pm 15^{\circ}\text{C}$ for future use microbiome studies
- Provide stool sample collection container and instructions on how to collect stool sample
- Provide instructions to women participants to avoid pregnancy through the 28 days from receipt of the last dose of vaccine.
- Confirm date and time for Visit 8

7.3.7 **VISIT 8 (~12 weeks post-dose 3 (window ±1 week)**

- Confirm ongoing consent prior to performing any study procedures. Conduct eligibility review. Review any SAEs that have occurred since the last visit as well as update the medical history and concomitant medications as necessary, to support an SAE.
- Record oral temperature, pulse, and blood pressure
- Targeted physical examination, if indicated based on review of medical history
- Collect approximately 15 mL of venous blood:
 - 2 mL for serum ELISA and neutralization assays
 - 13 mL for cryopreservation of PBMC, for memory B cell (5 mL) and effector T cell assays (8 mL)
 - Collect plasma from PBMC tubes
- Confirm date and time for Visit 9

7.4 **Final Study Visit**

7.4.1 **VISIT 9 (~6 months post-dose 3, window ±2 weeks)**

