## 9.7. Vital Signs and Physical Evaluations

The baseline value will be defined as the last value obtained prior to the first vaccination/dose of study product. If a participant has repeated vital sign measurements on the same day, the value from the last evaluation will be used for analysis. Post-baseline, in the case of multiple observations (for example, from supplemental visits), the assessment value that is closest to the scheduled visit window will be used in the analyses. All the recorded data will be listed. If observations have the same distance to the scheduled assessment, the latest one will be used.

Vital sign measurements include systolic blood pressure, diastolic blood pressure, pulse, and oral temperature. Grading scales for vital signs are presented in [Table 9](#). Vital signs were assessed at Day 1, Day 8, Day 15, Day 22, Day 29, Day 36, Day 57, Day 114 and Day 209 for Oral and Sublingual Cohorts and at Day 1, Day 8, Day 22, and Day 29 for Intradermal Cohorts. Vital signs will be tabulated by severity, visit, and treatment group ([Table 160](#), [Table 161](#), [Table 162](#), [Table 163](#), and [Table 164](#); [Listing 25](#)).

Physical Examinations were performed at screening to assess general wellness. The following body systems were assessed: head, eyes, ears, nose, and throat; lymph nodes; skin; pulmonary; cardiovascular; abdominal; neurological; and musculoskeletal systems. At subsequent visits including enrollment a targeted physical examination was conducted if indicated based on review of medical history. Findings will be presented in Listing 26.

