**15. SUMMARY OF CHANGES IN THE CONDUCT OF THE STUDY OR PLANNED ANALYSES****Changes to Study Conduct**

- At the request of the local (icddr,b) DSMB, collection of serum bilirubin at screening and Visit 6 and collection of ALT and creatinine at Visit 6 were added to the safety labs. These results were not obtained for Cohorts A through C which were enrolled prior to the request.
- Due to a country-wide lockdown instituted in Bangladesh to combat the COVID-19 pandemic all Cohort E participants did not receive a third dose of study product. Cohort D participant Visits 8 and 9 and Cohort E participant Visits 6 through 9 were not conducted and no further cohorts were enrolled due to the pandemic.

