### 14.3.5 Displays of Laboratory Results

**Figure 254: Laboratory Results by Scheduled Visits: Mean Changes from Baseline by Laboratory Parameter, and Treatment Group – Creatinine, Oral Cohorts**

*[Implementation note: The figure below is an example only. Groups presented will be Cohort A: Oral 5 µg dmLT, Cohort B: Oral 25 µg dmLT, and All Oral Cohorts: Placebo at Baseline and Study Days 36 and 57.]*

Figures with similar format:

**Figure 255: Laboratory Results by Scheduled Visits: Mean Changes from Baseline by Laboratory Parameter, and Treatment Group – Creatinine, Sublingual Cohorts**

*[Implementation note: Groups presented will be Cohort C: Sublingual 5 µg dmLT, Cohort D: Sublingual 25 µg dmLT, and All Sublingual Cohorts: Placebo at Baseline and Study Days 36 and 57.]*

**Figure 256: Laboratory Results by Scheduled Visits: Mean Changes from Baseline by Laboratory Parameter, and Treatment Group – Creatinine, Intradermal Cohort**

*[Implementation note: Groups presented will be Cohort E: Intradermal 0.3 µg dmLT and Cohort F: Intradermal Placebo at Baseline and Study Days 50 and 71.]*

**Figure 257: Laboratory Results by Scheduled Visits: Mean Changes from Baseline by Laboratory Parameter, and Treatment Group – Alanine Aminotransferase, Oral Cohorts**

*[Implementation note: Groups presented will be Cohort A: Oral 5 µg dmLT, Cohort B: Oral 25 µg dmLT, and All Oral Cohorts: Placebo at Baseline and Study Days 36 and 57.]*

**Figure 258: Laboratory Results by Scheduled Visits: Mean Changes from Baseline by Laboratory Parameter, and Treatment Group – Alanine Aminotransferase, Sublingual Cohorts**

*[Implementation note: Groups presented will be Cohort C: Sublingual 5 µg dmLT, Cohort D: Sublingual 25 µg dmLT, and All Sublingual Cohorts: Placebo at Baseline and Study Days 36 and 57.]*

**Figure 259: Laboratory Results by Scheduled Visits: Mean Changes from Baseline by Laboratory Parameter, and Treatment Group – Alanine Aminotransferase, Intradermal Cohort**

*[Implementation note: Groups presented will be Cohort E: Intradermal 0.3 µg dmLT and Cohort F: Intradermal Placebo at Baseline and Study Days 50 and 71.]*

**Figure 260: Laboratory Results by Scheduled Visits: Mean Changes from Baseline by Laboratory Parameter, and Treatment Group – Total Bilirubin, Sublingual Cohorts**

*[Implementation note: Groups presented will be Cohort D: Sublingual 25 µg dmLT and Cohort D: Placebo at Baseline and Study Days 36 and 57.]*

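### SAP Tables 142–144 and 160–164: the Max Severity Post Baseline rows set side by side cohorts with different numbers of scheduled assessments, so they are not a fair between-cohort comparison

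*SAP*

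**What the plan says.** The note under SAP Table 142, repeated in the later shells, says that the Max "rows indicate the maximum severity experienced by each subject at any time point post baseline, including unscheduled assessments". The Max block in Tables 142–144 lists Cohorts A to E and the pooled placebo groups. Tables 161–164 do the same for vital signs. Table 160's Max block stops at the sublingual cohorts.

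SAP section 15 explains why the cohorts differ. ALT, creatinine and bilirubin at Visit 6 were added at the local DSMB's request, and "These results were not obtained for Cohorts A through C which were enrolled prior to the request". Because of the lockdown, "Cohort D participant Visits 8 and 9 and Cohort E participant Visits 6 through 9 were not conducted".

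The per-visit blocks follow section 15. In Tables 142–144 the block for 7 days after dose 3 names only Cohort D and its own placebo, and the block for 28 days after dose 3 names A–D. In Tables 160–164 the Day 114 and Day 209 blocks omit D, and the blocks from dose 3 onward omit E.

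Other parts of the SAP do not follow it. Section 9.6 says Day 36 chemistry was evaluated in the oral and sublingual cohorts without exception. The Figure 254 note asks for Cohorts A and B "and All Oral Cohorts: Placebo at Baseline and Study Days 36 and 57". Figure 257 does the same, and Figures 255 and 258 ask for Day 36 in Cohort C as well as D.

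**The concern.** A worst-grade summary depends on how often a person is assessed. A further assessment can raise a person's maximum or leave it unchanged, but cannot lower it. A row that takes the maximum over whatever assessments exist, and prints the cohorts together, therefore mixes differences in risk with differences in follow-up.

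Laboratory adverse events are part of a primary endpoint (SAP 3.2.1). Cohort C against Cohort D (5 against 25 µg sublingual) is one of only two within-route dose contrasts left after early termination; the other is A against B. With 12 vaccinees per cohort, one extra flagged person moves a row by 1/12, or 8.3 percentage points.

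Two further rows are hard to interpret. The pooled sublingual placebo chemistry row combines 3 people with one draw and 3 with two, so it matches neither C nor D. The Cohort E chemistry rows can hold only unscheduled or early-termination values, and Protocol 7.6 allows unscheduled laboratory tests in order to evaluate an adverse event. Such values are selected on symptoms.

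**Working it through.** The SAP states no figure for these rows, so there is none to reproduce. The check is a count of scheduled assessments, then an illustration of what unequal counts do.

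**Chemistry inputs.** The Visit 6 panel is "2 mL for clinical safety labs: ALT (also known as SGPT), total bilirubin, and creatinine" (Protocol 7.3.5). The Visit 7 panel is "2 mL for clinical safety labs: CBC with differential for WBC, Hg, ANC, platelets; creatinine, albumin, and ALT" (Protocol 7.3.6). SAP section 15 removes Visit 6 chemistry from A–C and Visits 6–9 from E.

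**Vital-sign inputs.** For the oral and sublingual cohorts, "Vital signs were assessed at Day 1, Day 8, Day 15, Day 22, Day 29, Day 36, Day 57, Day 114 and Day 209" (SAP 9.7). For the intradermal cohort the days are 1, 8, 22 and 29. The definition "The baseline value will be defined as the last value obtained prior to the first vaccination/dose of study product" makes Day 1 the baseline. Section 15 removes Visits 8 and 9 from D.

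| Scheduled post-baseline assessments | A, B, C | D | E |
|---|---|---|---|
| ALT, creatinine | 1 (Day 57) | 2 (Days 36, 57) | 0 |
| Vital signs | 9 − 1 = 8 | 8 − 2 = 6 | 4 − 1 = 3 |

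For the any-chemistry row of Table 142, the protocol panels give 3 results per person in A–C (creatinine, albumin, ALT) and 3 + 3 = 6 in D.

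**One chemistry parameter, C against D.** Let p be the chance of a Grade 1 or higher value at one draw, the same in both cohorts. Let c be the chance that a person abnormal at one draw is abnormal at the other. The expected share flagged is p with one draw and 2p − pc with two, so the D:C ratio is 2 − c. Independence means c = p. The documents give neither p nor c, so a range is shown.

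| p (assumed) | C | D, independent | D, c = 0.5 | D, c = 1 |
|---|---|---|---|---|
| 1% | 1.0% | 2.0% | 1.5% | 1.0% |
| 2% | 2.0% | 4.0% | 3.0% | 2.0% |
| 5% | 5.0% | 9.8% | 7.5% | 5.0% |
| 10% | 10.0% | 19.0% | 15.0% | 10.0% |

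The ratio is 1.9 to 2.0 under independence, 1.5 at c = 0.5 and 1.0 at c = 1.

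**In people, 12 per cohort, independent draws.** At p = 2% the chance of at least one flagged person is 0.215 in C and 0.384 in D. The chances that D's count is above, equal to or below C's are 0.32, 0.54 and 0.14. At p = 5% the chance of at least one is 0.460 in C and 0.708 in D, and the three chances are 0.51, 0.31 and 0.18. With equal numbers of draws at p = 5% they would be 0.29, 0.42 and 0.29.

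**Vital signs.** Under independence the share flagged over k visits is 1 − (1 − p)^k.

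| p per visit (assumed) | A–C, k = 8 | D, k = 6 | E, k = 3 |
|---|---|---|---|
| 1% | 7.7% | 5.9% | 3.0% |
| 2% | 14.9% | 11.4% | 5.9% |
| 5% | 33.7% | 26.5% | 14.3% |
| 10% | 57.0% | 46.9% | 27.1% |

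**With shared visits only.** Chemistry at Day 57 gives one draw each in A–D, so the expected D:C ratio is 1.0 at equal risk. Vital signs at p = 5% become 26.5% in each of A–D over Visits 2–7 (6 visits), or 14.3% in each of A–E over Visits 2–4 (3 visits).

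**The case against.** The strongest reply is that the fair chemistry comparison is already in the tables. The Day 57 block for A–D stands above the Max row, Cohort D's Day 36 block is separate, section 15 gives the reason, and the listings show the planned time point and study day of each result. The study tests no hypothesis (SAP 6.8), and placebo was included for blinding and not as a comparison group (SAP 4.2). No comparison of the Max rows is planned. All of this stands. It limits the harm, but it does not make an unfootnoted row comparable across its columns.

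The size can also be challenged. The two draws are 21 days apart in the same person, so independence is the extreme case. Eligibility required ALT and creatinine no higher than the upper limit of normal (Protocol Appendix B), while Grade 1 starts at 1.25 and 1.1 times that limit (Appendix C), so low per-draw rates are plausible. At 2%, the expected numbers flagged are 0.24 of 12 in C and 0.48 in D. Repeated pulse and blood-pressure readings in one person are also unlikely to be independent, so the vital-sign table shows the upper end of the gap.

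A reader might infer that the higher sublingual dose must look worse by construction. The documents do not support that. The chemistry bias is one of expectation, it vanishes if abnormality persists, and at low rates a tie is the likeliest result. For vital signs the bias favours D over C.

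A reader might also infer that the any-time maximum should be cut back to shared visits. That could remove a genuine graded value from the safety summary, so the row should stay.

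**Conclusion.** The concern holds as one of comparability in descriptive safety tables. The assessment counts follow from the schedule and SAP section 15, and the direction of bias at equal true risk follows from the definition of a maximum: D at or above C for ALT and creatinine, D at or below C for vital signs, and E at or below every other cohort for vital signs. The counts are of scheduled assessments; unscheduled and early-termination values also enter the rows.

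The chemistry inflation lies between none and about 2-fold. Its place in that range depends on within-person persistence and on per-draw rates that the documents do not give. No error rate is affected. The chemistry count rests on section 15 and the per-visit blocks of Tables 142–144, which agree with each other. SAP 9.6 and Figures 254, 255, 257 and 258 conflict with them and must be reconciled.

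**What to change.** - Keep the any-time maximum in Tables 142–144 and 160–164 as a safety capture. Label it with the number of scheduled assessments per cohort and state that it is not for between-cohort comparison. For the pooled sublingual placebo chemistry row, state that 3 people had one draw and 3 had two.
- Base between-cohort comparison on shared scheduled visits. For chemistry, use the existing Day 57 block for A–D and keep Cohort D's Day 36 block separate. For vital signs, add a maximum over Visits 2–4 for A–E and one over Visits 2–7 for A–D.
- Show Cohort E chemistry as not assessed, and list any unscheduled values.
- Remove Day 36 from Figures 254 and 257. In Figures 255 and 258 show Day 36 for Cohort D and its own placebo only.
- Reconcile SAP 9.6 with SAP section 15 on which cohorts had Day 36 chemistry.

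The cost is minor programming: changes to eight table shells and four figure shells, and one text correction. No new data are needed.
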